9.4 STATISTICAL ANALYSES

9.4.1 GENERAL APPROACH

In general, continuous data will be summarized with descriptive statistics (number of patients, mean, standard deviation, median, minimum, and maximum) and will be analyzed using analysis of variance (ANOVA) techniques or 2-sample t-tests for between-group comparisons, and paired t-tests for within-group analyses. Categorical variables will be summarized by sample size (N),

frequency count, and percent, and they will be analyzed using Pearson's chi-square test or Fisher's exact test (if the expected cell count is less than 5 in 25% or more of the cells). Ordinal variables will be analyzed using the Wilcoxon rank-sum test for between-treatment comparisons and the sign-rank test for within-treatment comparisons.

Cohort 1: Efficacy (MGD):

The primary efficacy variables for MGD are change from baseline to month 3 in MGS, number of MGYLS, and the proportion of patients improving on both a gland score (e.g., MGS or MGYLS) and a patient reported outcome measure (e.g., OSDI). A patient will be considered to be a meibum quality responder at a post-randomization visit if the MGS score in the study eye is > 12 , MGYLS score > 2 , or MGYOLS score > 2 . The visit for the primary variable is month 3 and the primary analysis population is mITT. Statistical tests will be performed for each AZR-MD- 001 group versus vehicle group. Odds ratio along with 95% CI will be obtained by pairwise comparisons of the proportion of responders for each AZR-MD- 001 group versus vehicle group using the Logistic Regression method stratifying by baseline MGS score for the qualified eye (i.e., < 6 or ≥ 6 and ≤ 12) and duration of disease (i.e., < 5 years or ≥ 5 years). There will be no alpha adjustment for the multiple tests for the pairwise comparisons.

Cohort 1: Efficacy (Evaporative DED):

The primary efficacy variables for evaporative DED are change from baseline to month 3 in Tear Break-up Time (TBUT), OSDI, eye dryness measured using a visual analogue scale (VAS), and proportion of patients with a Total OSDI change from baseline > 4.5 , the known minimally important clinical difference (MICD) for early to moderate disease, at Month 3. A patient will be considered to be an evaporative DED responder at a post-randomization visit if TBUT > 10 seconds, a Schirmer's test ≥ 10 mm, a Total OSDI < 13 , a SPEED Score < 6 , or an Average VAS or Worst VAS score decreased by ≥ 5 is observed.

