8.2.1. Key Secondary Efficacy Analyses

Proportion of MGYLS responders based on change from baseline ≥ 5 will be analyzed through Month 3 using a CMH test to compare the proportions between each AZR-MD-001 group and placebo, stratifying by disease duration category (i.e., <5 or ≥ 5 years) and baseline MGS score category (<6 or ≥ 6 and ≤ 12). If the CMH statistic is not estimable, the treatment difference will be evaluated using Pearson's chi-square test, or Fisher's exact test (if the expected cell count is <5 for at least 25% of the cells).

The following pseudocode will be used:

```
PROC FREQ data=xxx;  
  BY visit;  
  TABLE baseMGS * duration * treatment * response/CMH;  
  ODS OUTPUT CMH = outcmh (where=(STATISTIC=2));
```

```
Run;

PROC FREQ data=xxx;
  BY visit;
  TABLE treatment * response/EXACT;
  ODS OUTPUT CHISQ = outc (where=(STATISTIC='Chi-Square'))
             FISHERSEXACT=outf (where=(NAME1='XP2_FISH'));
Run;
```

Proportion of OSDI responders based on OSDI total score <13 will be analyzed through Month 3 as described for the proportion of MGYLS responders, using a CMH test (or chi-square/Fisher's Exact if CMH is not estimable) to evaluate the difference between treatments, controlling for duration of disease category and baseline MGS score category.

Change from baseline in SPEED score at Day 14, Month 1.5 and Month 3 will be analyzed as described for MGYLS in [Section 8.1.1](#).

Change from baseline in Eye Dryness VAS at Day 14, Month 1.5 and Month 3 will be analyzed as described for MGYLS in [Section 8.1.1](#).

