Change from baseline in Average VAS and Worst VAS at Day 14, Month 1.5 and Month 3 will be analyzed as described for MGYLS in [Section 8.1.1](#).

Proportion of Average VAS responders based on decrease ≥ 5 and proportion of Worst VAS responders based on decrease ≥ 5 will be analyzed through Month 3 as described for the proportion of MGYLS responders, using a CMH test (or chi-square/Fisher's Exact if CMH is not estimable) to evaluate the difference between treatments, controlling for duration of disease category and baseline MGS score category.

Change from Schirmer's assessment at Day 14, Month 1.5 and Month 3 will be analyzed as described for MGYLS in [Section 8.1.1](#).

Proportion of Schirmer's ≥ 10 mm responders will be analyzed through Month 3 as described for the proportion of MGYLS responders, using a CMH test (or chi-square/Fisher's Exact if CMH is not estimable) to evaluate the difference between treatments, controlling for duration of disease category and baseline MGS score category.

Change from baseline in Burning/Stinging VAS, Itching VAS, Foreign Body Sensation VAS, Eye Discomfort VAS, Photophobia VAS, and Pain VAS at Day 14, Month 1.5 and Month 3 will be analyzed as described for MGYLS in [Section 8.1.1](#).

Proportion of patients with clinical cure, defined as having MGYLS change from baseline ≥ 5 and OSDI total score < 13 , will be analyzed through Month 3 as described for the proportion of MGYLS responders, using a CMH test (or chi-square/Fisher's Exact if CMH is not estimable) to evaluate the difference between treatments, controlling for duration of disease category and baseline MGS score category.

Eyelid margin erythema and telangiectasias results will be summarized by time point, in conjunction with other findings from the slit lamp examination. Actual values and shifts from baseline through Month 3 will be summarized by parameter and time point. Changes from baseline will be analyzed at each time point using CMH statistics to evaluate the differences between each AZR-MD-001 treatment group and placebo, controlling for baseline value, using the following pseudocode:

```
PROC FREQ data=xxx;
  BY visit;
  TABLE treatment * base * result / CMH;
  ODS output CMH=outcmh (where=(ALTHYPOTHESIS='General Association'));
run;
```

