Corneal and conjunctival staining (sodium fluorescein corneal staining and lissamine green conjunctival staining) are assessed on a 6-point scale using grades 0, I, II, III, IV, and V, and are summarized by grade and shift from baseline. Shift from baseline through Month 3 will be analyzed using CMH statistics as described for eyelid margin erythema and telangiectasias.

8.3.2. Exploratory Efficacy Analyses Performed at Month 6

These analyses will be performed using the ITT, mITT, and PP6 sets, as indicated. P-values will be provided for descriptive purposes only.

Change from baseline in MGYLS at Month 4.5 and Month 6 will be analyzed as described for MGYLS in [Section 8.1.1](#). This analysis will utilize multiple imputation based on data from the entire 6-month study duration, as described in [Section 5.3.1.2](#), on the ITT, mITT, and PP6 sets. It will be repeated using LOCF on the ITT Set, as described in [Section 8.1.2.1](#).

Change from baseline in OSDI total score at Month 4.5 and Month 6 will be analyzed as described for MGYLS in [Section 8.1.1](#). This analysis will utilize multiple imputation based on data from the entire 6-month study duration, as described in [Section 5.3.1.2](#), on the ITT, mITT, and PP6 sets. It will be repeated using LOCF on the ITT Set, as described in [Section 8.1.2.1](#). Additionally, an analysis of potentially confounding medication, as described in [Section 8.1.2.2](#), will be performed at Month 6, utilizing the ITT Set with multiple imputation.

Proportion of MGYLS responders based on change from baseline ≥ 5 at Month 4.5 and Month 6 will be analyzed as described in [Section 8.2.1](#), using a CMH test (or chi-square/Fisher's Exact if CMH is not estimable) to evaluate the difference between treatments, controlling for duration of disease category and baseline MGS score category.

Proportion of OSDI responders based on OSDI total score < 13 at Month 4.5 and Month 6 will be analyzed as described in [Section 8.2.1](#), using a CMH test (or chi-square/Fisher's Exact if CMH is not estimable) to evaluate the difference between treatments, controlling for duration of disease category and baseline MGS score category.

Change from baseline in SPEED score at Month 4.5 and Month 6 will be analyzed as described for MGYLS in [Section 8.1.1](#).

Change from baseline in individual VAS scores, Average VAS, and Worst VAS at Month 4.5 and Month 6 will be analyzed separately as described for MGYLS in [Section 8.1.1](#).

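### The CMH 'General Association' statistic chosen for graded signs ignores grade order and, once the table order is corrected, costs about 9 to 24 points of power against a one-directional shift

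*SAP*

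**What the plan says.** SAP 8.3.1 analyses changes in eyelid margin erythema and telangiectasia by CMH at each time point. The stated aim is "to evaluate the differences between each AZR-MD-001 treatment group and placebo, controlling for baseline value". The pseudocode requests "TABLE treatment * base * result / CMH" and keeps only the row selected by "ODS output CMH=outcmh (where=(ALTHYPOTHESIS='General Association".

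Staining with fluorescein and lissamine green is "assessed on a 6-point scale using grades 0, I, II, III, IV, and V", and the SAP continues: "Shift from baseline through Month 3 will be analyzed using CMH statistics as described for eyelid margin erythema and telangiectasias". SAP 8.3.2 carries both analyses to Months 4.5 and 6 by reference.

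Protocol 9.4.1 says: "Ordinal variables will be analyzed using the Wilcoxon rank-sum test for between-treatment comparisons". The protocol synopsis and Section 9.4.5 are looser and allow either CMH or Wilcoxon for ordinal variables, without naming a CMH statistic. SAP Section 12, which lists some of the changes from the protocol, does not mention ordinal grades.

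**The concern.** PROC FREQ prints three CMH statistics. General Association uses no scores: it asks whether the distribution of grades differs in any way and has (rows − 1) × (columns − 1) degrees of freedom. For one dose against placebo that is 5 df on a six-grade scale. Row Mean Scores Differ uses the order of the columns and has 1 df for two arms.

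A treatment that helps should move grades towards the mild end. General Association spreads its sensitivity over every possible pattern, so it is less likely to detect such a shift. What is at stake is the chance of seeing a real improvement in the lid-margin and ocular-surface signs.

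**Working it through.** **1. What the documents supply.** Neither document states a power for these tests, so there is no planned figure to reproduce. The usable inputs are:

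- 75 patients per arm, allocated 1:1:1 (SAP 2.3.1 and 2.4);
- two-sided alpha of 0.05 (Protocol 9.4.6);
- six ordered grades for staining (SAP 8.3.1);
- exclusion of corneal staining of grade 3 or above (Protocol 5.2).

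The documents do not give the number of levels for erythema or telangiectasia, the grade distributions or an effect size. These are assumptions below, with a range shown.

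**2. What the table request tests.** In PROC FREQ the last two variables form the table and earlier ones are strata. "TABLE treatment * base * result / CMH" therefore cross-tabulates baseline grade against result grade within each treatment. The responder code in SAP 8.2.1 has the right order: "TABLE baseMGS * duration * treatment * response/CMH" puts treatment in the rows.

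The consequence was simulated with 1,000 runs per case, 75 per arm and two arms. Assumptions: four result grades, and baseline grades 0/1/2 in 35/40/25%. The table gives the rejection rate of the request as written.

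| Link of result to baseline (logits per grade) | General Association, no treatment effect | General Association, log-OR 1.0 | Row Mean Scores, no treatment effect |
|---|---|---|---|
| 0 | 4.7% | 5.9% | 4.5% |
| 0.5 | 43.1% | 38.2% | 61.2% |
| 1.0 | 98.3% | 98.0% | 99.6% |
| 1.5 | 100% | 100% | 100% |

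The rates follow the baseline link and hardly respond to treatment. Changing only the statistic does not cure this.

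**3. Power with treatment in the rows, analytic.** Give both statistics the same noncentrality λ, as for a shift lying along the scores. For 80% power at 1 df (critical value 3.84), λ = 7.85. Power at k df is P(χ²ₖ(λ) > critical value). The sample-size ratio is the λ needed for 80% at k df, divided by 7.85.

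| Grades in use | df | Critical value | Power at λ = 7.85 | λ for 80% | Ratio of N |
|---|---|---|---|---|---|
| 2 | 1 | 3.84 | 80% | 7.85 | 1.00 |
| 3 | 2 | 5.99 | 71% | 9.63 | 1.23 |
| 4 | 3 | 7.81 | 64% | 10.90 | 1.39 |
| 5 | 4 | 9.49 | 60% | 11.94 | 1.52 |
| 6 | 5 | 11.07 | 56% | 12.83 | 1.63 |

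The loss from 80% is thus 9 points at three grades (80 − 71) and 24 at six (80 − 56).

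**4. Power with treatment in the rows, simulated.** There were 1,500 runs per case, with 75 per arm, strata by baseline grade (35/40/25%) and a proportional-odds shift.

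| Grades | log-OR | General Association | Row Mean Scores |
|---|---|---|---|
| 3 | 0.8 | 55.3% | 66.9% |
| 4 | 0.8 | 49.2% | 63.8% |
| 6 | 0.8 | 48.4% | 73.7% |
| 3 | 1.0 | 72.6% | 82.5% |
| 4 | 1.0 | 71.1% | 84.9% |
| 6 | 1.0 | 67.2% | 89.7% |

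The gap runs from about 10 points (82.5 − 72.6) to 25 points (73.7 − 48.4), in line with step 3. With no treatment effect, both statistics reject in 4.0% to 5.9% of runs, so validity is not at issue once the order is right.

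**The case against.** The strongest objection is that the loss is conditional. As coded, the analysis does not test treatment, so it is not yet a weaker treatment test. That stands: the table order is the more serious defect, and the figures here apply only after it is corrected. Correcting the order alone would still leave the inefficient statistic in place.

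Four further points limit the size and wording:

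- **Scale.** No scale is given for erythema or telangiectasia. If either is recorded as present or absent, both statistics are 1-df tests and nothing is lost. Upper corneal grades may be sparse because of the entry limit, so the effective degrees of freedom may be well below 5.
- **Protocol departure.** A reader might infer an undisclosed departure from the protocol. The documents do not support that firmly: the synopsis and Section 9.4.5 allow CMH for ordinal variables, Protocol 9.4.2 leaves details of other efficacy analyses to the SAP, and SAP Section 12 claims to list only some changes. What remains is that General Association does not use the order, whereas the test in 9.4.1 does.
- **Direction.** A reader might infer that only General Association is blind to direction. Row Mean Scores Differ is also an unsigned chi-square. Under either, direction is read from the planned grade and shift summaries.
- **Other alternatives.** General Association is a valid omnibus test and need not be weaker for a non-monotone effect. A shift towards milder grades is, however, the effect of interest here.

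**Conclusion.** The point holds in a limited form. With treatment correctly placed in the rows, General Association loses about 9 points from 80% power if three grades are in use, 16 with four and 24 with six. The analytic figures assume a one-directional shift captured by the scores; the simulations assume proportional odds and the baseline mix stated above. The six-grade figure is relevant to staining only if most grades occur, and should not be read across to all four outcomes.

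A reader might infer that the trial's efficacy conclusion is weakened. It is not. These endpoints are exploratory and outside the testing hierarchy in SAP 8.1.1, no power is promised for them, and SAP 8.3.2 presents the Month 4.5 and Month 6 p-values as descriptive. This is a free improvement to make alongside the correction of the table order.

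**What to change.** In SAP 8.3.1, and so in 8.3.2 by reference:

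1. Restrict each run to one dose plus placebo.
2. Request `TABLE base * treatment * result / CMH SCORES=MODRIDIT`.
3. Keep the row with `ALTHYPOTHESIS='Row Mean Scores Differ'`. With modified ridit scores this is a Wilcoxon test stratified by baseline grade, in line with Protocol 9.4.1.
4. State the grading scale for erythema and telangiectasia, and record the choice of CMH statistic in Section 12.

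The order and the statistic must change together: changing only the statistic still tests baseline against result. The cost is a few lines of code and a sentence or two of text before unmasking, with no effect on data collection or sample size.

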9. ANALYSIS OF PHARMACOKINETICS

Pharmacokinetics are not measured in the Expansion Cohort.

10. SAFETY

The Safety Set will be used for safety analyses reports. Safety will be assessed based on adverse events, vital signs, BCVA (Logarithmic visual acuity chart), biomicroscopy, ophthalmoscopy, IOP, and conjunctival hyperemia (redness).

The primary safety analysis will be performed after all patients have completed the Month 3 visit or discontinued from the study. An additional 3-month safety follow-up (including Month 4.5 and Month 6 visits) will be conducted, and supplemental safety results will be produced after the completion of the Month 6 visits.

A combined analysis of Cohort 1 and Expansion Cohort data will not be produced, as Cohort 1 includes different dosing regimens (once daily vs. twice weekly) as well as including different treatments (AZR-MD-001 0.1%, vehicle).

10.1. Extent of Exposure and Compliance

During the Baseline visit, the patient will be dispensed Vaseline, which will be administered while on site and the prospective patient will be observed by the physician or a designee. Eligible patients will also be dispensed randomized study medication (AZR-MD-001 or placebo), which will be administered twice weekly at home. Patients are expected to apply the first application of randomized study medication on the same date, in the evening.

Application, dispensation, and return of randomized study treatment will be listed chronologically by patient and visit. A separate listing of Physician Observation of Drug Application, for observation of Vaseline applied during the Baseline visit, will be provided.

Compliance for randomized study treatment, in the form of numbers of doses administered and missed, is collected in 6-week intervals. Approximately 12 doses are expected to be administered during each of those 6-week periods, but slightly more or less may be expected depending on actual visit dates and visit windows. The expected number of doses for a given period is calculated as $2 \times (\text{end date} - \text{start date} + 1) / 7$, rounded to the nearest whole number. Compliance is then calculated as $100 \times (\text{number of doses taken}) / (\text{number of expected doses})$.

Overall compliance for the 3 month study period will be based on the expected numbers of doses calculated as $2 \times ([\text{Month 3 visit date or date of discontinuation}] - [\text{date of first dose}] + 1) / 7$, for the 3 month study period, and $2 \times ([\text{Month 6 visit date or date of discontinuation}] - [\text{date of first dose}] + 1) / 7$, for the 6 month period including follow-up. The number of patients with compliance <80%, 80%-120%, and >120% will be tabulated.

For the safety follow-up period, if the final study drug is returned after the Month 6 visit (based on the visit date as compared to the final study drug return date), compliance will be calculated based on the Month 6 visit date. If dates of dispensation or return are not recorded on the eCRF (e.g., visit restrictions were in place and study treatment was mailed to patients), compliance calculations will be based on the assumption that 12 doses should have been administered.

Compliance through the Month 3 visit will be presented at the completion of the 3-month study period. Compliance through the end of the safety follow-up period (i.e., through Month 6) will be presented as part of the supplemental safety analyses.

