6.2 PREPARATION/HANDLING/STORAGE/ACCOUNTABILITY

6.2.1 ACQUISITION AND ACCOUNTABILITY

Whilst patients are dosed at site (i.e., Cohort 1 all visits, and practice dose at the baseline visit only of the Expansion Cohort), they will administer their study treatment under medical supervision. The date and time of each dose administered in the clinic will be recorded in the source documents. The dose of study treatment and study subject identification will be confirmed at the time of dosing by a member of the study site staff.

Patients will be instructed on proper instillation and storage of study drug at the end of each visit, and will be given written instructions and may also watch an instructional video at the baseline visit. The used study drug tubes will be collected at each visit from baseline up to and including study exit (along with any unused tubes) to assess dosing and symptom assessment compliance. Dosing compliance will be based off of the used and unused tube count. If the subject is less than 80% or more than 125% compliant with dosing based on the expected number of used tubes, then the subject will be deemed non-compliant and a deviation should be recorded.

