5.2. Key Definitions

5.2.1. Date of First Dose of Study Treatment

The date of first dose of study treatment will be the date of the Baseline visit, at which the randomized study treatment is dispensed. Patients are to be instructed to apply the first dose at home that evening. Patients who do not have confirmation of study treatment administration (defined as non-zero number of doses taken, on a study drug compliance eCRF at the Month 1.5 visit) will not have a date of first dose defined. If a patient takes zero doses before the Month 1.5 visit but does take subsequent doses, the date of first dose will reflect the date of dispensation of the first study treatment applied.

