5.2.3. Study Day

Study day is calculated as (date - first dose date of study medication +1) for dates on or after first dose, and (date - first dose date) for dates before the first dose date. Therefore, the first dose date is Study Day 1, and the day immediately prior is Study Day -1. The first dose date of study medication will be based on the application of Vaseline while onsite during the Baseline visit. The first application of randomized study medication is expected to be applied that evening.

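### SAP 10.1 can band a patient who missed the first six weeks of treatment as 80%-120% compliant, because its denominator starts at a first-dose date that SAP 5.2.1 moves and SAP 5.2.3 defines differently

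*SAP*

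**What the plan says.** **Overall compliance.** SAP 10.1 says: "Overall compliance for the 3 month study period will be based on the expected numbers of doses calculated as" 2 × (Month 3 visit or discontinuation date − date of first dose + 1)/7, with Month 6 in place of Month 3 for the longer period. It then tabulates overall results: "The number of patients with compliance" below 80%, from 80% to 120%, and above 120%.

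**Date of first dose.** SAP 5.2.1 normally sets this at the Baseline visit. For a patient with no doses before Month 1.5 who does start later, "the date of first dose will reflect the date of dispensation of the first study treatment applied". SAP 5.2.3, which defines study day, says: "The first dose date of study medication will be based on the application of Vaseline while onsite during the Baseline visit". SAP 10.1 does not say which definition it uses.

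**Interval compliance.** Doses taken and missed are collected in six-week intervals. "Approximately 12 doses are expected to be administered during each of those 6-week periods", and the expected number is 2 × (end − start + 1)/7, "rounded to the nearest whole number". Where dispensation or return dates are not on the eCRF, "compliance calculations will be based on the assumption that 12 doses should have been administered".

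**Protocol limit.** Protocol 6.2.1 measures compliance by tube count and requires a deviation: "If the subject is less than 80% or more than 125% compliant with dosing based on the expected number of used tubes". SAP section 12, which lists changes from the protocol, mentions neither the move from tubes to doses nor the different upper limit.

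**The concern.** A compliance percentage should show how much of the assigned treatment was taken. If the denominator starts only when the patient starts, a long initial gap disappears and the patient looks fully adherent. SAP 5.2.1 foresees exactly this patient and SAP 10.1 inherits its date. Because SAP 5.2.3 offers another anchor, two programmers could each follow the plan and put the same patient in different bands.

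What is at stake is Table 17 (exposure and compliance through Month 3), Table 17.1 (its Month 6 counterpart) and the matching listings, which readers use to judge how much drug lies behind the efficacy and safety results. The protocol's tube count is too coarse to stand in for a dose count: tubes are used for 30 days, so 84 days spans about three tubes and one tube is about a third of the total.

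**Working it through.** **Inputs.** Scheduled visits fall 42, 84 and 168 days after Baseline for Month 1.5, 3 and 6 (SAP 5.1). Windows are ±7 days at Month 1.5 and 4.5 and ±2 days at Month 3 and 6 (SAP Table 2). Dosing is twice weekly. Expected doses E = 2 × (end − start + 1)/7 (SAP 10.1).

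**Plan's own figure.** For a 42-day interval, E = 2 × 43/7 = 12.29, which rounds to 12. The stated expectation is reproduced.

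**Late starter, scheduled days.** No doses to day 42, then full twice-weekly dosing from treatment dispensed on day 42.

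| | Doses taken | E from day 42 (5.2.1) | Compliance | E from Baseline (5.2.3) | Compliance |
|---|---|---|---|---|---|
| Month 3 | 12 | 2 × 43/7 = 12.29 | 97.7% | 2 × 85/7 = 24.29 | 49.4% |
| Month 6 | 36 | 2 × 127/7 = 36.29 | 99.2% | 2 × 169/7 = 48.29 | 74.6% |

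Rounding the expected doses gives 100% against 50% at Month 3, and 100% against 75% at Month 6. The band changes from below 80% to 80%-120% at both times.

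**Late starter, across the Month 3 windows.**
- Month 1.5 on day 49, Month 3 on day 82, 9 doses: 9/9.71 = 92.6%, against 9/23.71 = 38.0% from Baseline.
- Month 1.5 on day 35, Month 3 on day 86, 15 doses: 15/14.86 = 101.0%, against 15/24.86 = 60.3%.
- Month 1.5 on day 49, Month 3 on day 86, 11 doses: 11/10.86 = 101.3%, against 11/24.86 = 44.3%.

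The change of band does not depend on exact visit timing.

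**Fixed default of 12.** The windows allow 35 to 49 days from Baseline to Month 1.5 and 33 to 51 days for each later interval (for example 82 − 49 = 33 and 86 − 35 = 51).
- 33 days: E = 2 × 34/7 = 9.71, rounded to 10; 10/12 = 83.3%.
- 49 days: E = 2 × 50/7 = 14.29, rounded to 14; 14/12 = 116.7%.
- 50 or 51 days: E = 14.57 or 14.86, rounded to 15; 15/12 = 125%.

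So full adherence by the SAP's formula reads 83% to 125% in-window. Only 50- and 51-day intervals exceed 120%, and none falls below 80%. Counting actual dosing evenings, a 33- to 35-day interval may hold only 9 doses, which is 75%.

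Errors are larger outside those limits. An out-of-window 56-day interval with 16 of 16 doses reads 16/12 = 133%. An exit on day 21 with all 6 due doses reads 6/12 = 50% if the default applies to that interval. The overall figure for that exit is 6/(2 × 22/7) = 6/6.29 = 95.5%, because it uses the discontinuation and first-dose dates.

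**The case against.** **Counting from treatment start is a recognised convention.** It describes adherence once treatment has begun, and preferring randomization is partly a matter of choice. That is fair, but the plan does not state the convention, and SAP 5.2.3 points the other way. The missed weeks are also not invisible: the first interval on its own would show 0 doses taken, and compliance is listed by patient. That stands and limits the harm, but it does not correct the overall figure.

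**The shift is conditional.** It needs the first treatment used to have been dispensed at Month 1.5. If the patient belatedly opened a tube dispensed at Baseline, SAP 5.2.1 leaves the date at Baseline and the result is 49.4%. This stands, and it means that even within 5.2.1 the band depends on which tube was opened.

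**The 12-dose default.** A reader might infer that patients sent drug by mail will be misbanded in Table 17. The documents do not support that. The trigger is unrecorded dates, with mailing only an example. Twelve is one interval's expectation, while the banding sentence follows the overall formula, which needs no dispensation or return date for a patient who started at Baseline. The default also sits in a paragraph that opens with the safety follow-up period, so its reach is unclear.

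**120% against 125%.** A reader might infer that the SAP contradicts the protocol. It does not: the protocol figure is a tube-count trigger for a deviation, and the SAP figure is a band for tabulating doses that carries no label of non-compliance. A dose percentage cannot be tested against the tube limit, and adopting one number would not reconcile the two measures. What remains is an undocumented change of metric and cut-off.

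**Conclusion.** The point holds for the overall compliance figure. Read with SAP 5.2.1, SAP 10.1 removes an untreated first six weeks from the denominator and moves the patient from below 80% to 80%-120%, at Month 3 (97.7% against 49.4%) and at Month 6 (99.2% against 74.6%). Read with SAP 5.2.3, it does not. The plan must settle which applies. The figures assume scheduled visit days, full dosing after the late start, and first use of treatment dispensed at Month 1.5.

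The 12-dose default is a lesser weakness, mainly in interval compliance. The 120% and 125% limits are a difference to reconcile or explain.

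The effect is confined to the compliance tables and listings, and the number of patients is likely to be small, though the documents give no figure. A reader might infer that the efficacy results are exposed. The documents do not support that: the primary analysis uses the ITT Set, the per-protocol sets depend on Grade 4 or 5 deviations, and no efficacy analysis uses the SAP 10.1 percentage directly.

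**What to change.** 1. In SAP 10.1, count expected doses for overall compliance from the Baseline/randomization date for every patient, whatever first-dose date 5.2.1 or 5.2.3 gives.
2. Where dispensation or return dates are unrecorded but a visit or discontinuation date exists, put that date into the interval formula. Keep 12 only when no date exists. SAP 10.1 already substitutes the Month 6 visit date when the last drug is returned later, so this extends an existing rule. State also whether the default can enter the overall figure.
3. In SAP section 12, record that the protocol's limit is by tube count (above 125%) and the SAP's band is by dose count (above 120%), and either reconcile the two or explain the difference.

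The cost is three wording edits, best made before the Month 3 database freeze. No new data are needed. A few patients may move to a less favourable band.
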